### **Hospitalization**

For reports of hospitalization, it is the sign, symptom or diagnosis which led to the hospitalization that is the serious event for which details must be provided.

Any event requiring hospitalization or prolongation of hospitalization that occurs during the study must be reported as a serious adverse event, except hospitalizations for the following:

- Hospitalizations not intended to treat an acute illness or adverse event (e.g., social reasons such as pending placement in long-term care facility)
- Surgery or procedure planned before entry into the study. [Note: Hospitalizations that were planned before the start of data collection and where the underlying condition for which the hospitalization was planned has not worsened will not be considered serious adverse events. Any adverse event that results in a prolongation of the originally planned hospitalization is to be reported as a new serious adverse event.]

### **Life-Threatening Conditions**

Disease progression should not be recorded as an adverse event or serious adverse event term; instead, signs and symptoms of clinical sequelae resulting from disease progression/lack of efficacy will be reported if they fulfill the serious adverse event definition.

#### **8.2.5 Expected Adverse Events**

An adverse event (AE) is considered "expected" if:

- For approved and marketed drugs or devices, those adverse events are described in the approved Package Insert (Label).
- For investigational new drugs or devices, those adverse events are described in the FDA Investigator's Brochure.
- In clinical research studies, information on expected adverse events is also summarized in the protocol and in the consent document. See section 9.1 and 9.2 for the list of expected adverse events related to the drugs under study.

#### **8.2.6 Unexpected Adverse Event**

An adverse event (AE) is considered "unexpected" if it is not described in the Package Insert, Investigator's Brochure, in published medical literature, in the protocol, or in the informed consent document.

---

**8.2.7 Pregnancy**

Any subject who becomes pregnant during the study must promptly discontinue further study treatment.

All study subject pregnancies occurring during the study participation or within 5 months of last dose must be reported to the Coordinating Center within the same time lines as for an SAE even if the patient was discontinued from the study. All pregnancies should be followed through to outcome (spontaneous miscarriage, elective termination, ectopic pregnancy, normal birth or congenital abnormality) whenever possible. The Coordinating Center should be notified once the outcome of the pregnancy is known. Follow-up information regarding the outcome of the pregnancy and any postnatal sequelae in the infant will be required.

Pregnancy itself is not regarded as an adverse event unless there is a suspicion that the investigational product under study may have interfered with the effectiveness of a contraceptive medication. Congenital abnormalities/birth defects, spontaneous miscarriages and abnormal pregnancy outcomes (e.g. spontaneous abortion, fetal death, stillbirth, congenital anomaly, ectopic pregnancy) should be reported and handled as SAEs. Elective abortions without complications should not be handled as AEs.

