3.1.7 Creatine phosphokinase  $\leq 2.5 \times$  institutional ULN

3.1.8 Women must be postmenopausal or have a negative urine or serum pregnancy test within 28 days of study treatment.

Postmenopausal is defined as any of the following:

- Amenorrheic for 1 year or more following cessation of exogenous hormonal treatments
- Luteinizing hormone (LH) and Follicle stimulating hormone (FSH) levels in the post-menopausal range for women under 50
- radiation-induced oophorectomy with last menses  $>1$  year ago
- chemotherapy-induced menopause with  $>1$ -year interval since last menses
- surgical sterilization (bilateral oophorectomy or hysterectomy)

3.1.9 Women of childbearing potential must agree to use adequate contraception from signing informed consent to at least 6 months after the last dose of study treatment. ([see Appendix B for acceptable methods])

3.1.10 Men must agree to use barrier contraception or abstinence and not donate sperm during treatment and for 5 months after the last dose of study treatment. Female partners of male patients should also use a highly effective form of contraception ([see Appendix B for acceptable methods]) if they are of childbearing potential.

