## 5.0 TREATMENT PLAN

### 5.1 Treatment Dosage and Administration

Protocol treatment must start within 14 business days of registration to the study.

Trabectedin 1.1 mg/m^2 will be administered intravenously over a 24-hour continuous infusion once every 21 days. Actual body weight from screening will be used to calculate dose. If weight changes by more than 10% from baseline, recalculate the dose.

Olaparib 150 mg tablets will be taken orally twice daily with a cycle length of 21 days. Olaparib should be taken at the same time every day, 12 hours apart with one glass of water. Olaparib can be taken with or without food. Tablets should be taken whole, not crushed or mixed into food. It is prohibited to consume grapefruit juice while on olaparib therapy. If vomiting occurs shortly after the olaparib tablets are swallowed, the dose should only be replaced if all of the intact tablets can be seen and counted. Should any patient enrolled on the study miss a scheduled dose for whatever reason (e.g., as a result of forgetting to take the tablets or vomiting), the patient will be allowed to take the scheduled dose up to a maximum of 2 hours after that scheduled dose time. If greater than 2 hours after the scheduled dose time, the missed dose is not to be taken and the patient should take their allotted dose at the next scheduled time.

Patients will be requested to maintain a medication diary of each dose of medication. The medication diary should be returned and/or reviewed by clinic staff at each scheduled clinic visit during the course of treatment.

REGIMENT DESCRIPTION					
Agent	Pre-medications; Precautions	Dose	Route	Schedule	Cycle Length
Trabectedin	Pre-medicate with dexamethasone 20 mg IV approximately 30 min prior to trabectedin. Pre-medicate with palonosetron 0.25 mg IV (or similar anti-emetic per institutional guidelines) prior to trabectedin	1.1 mg/m 	IV continuous infusion over 24 hours (+/- 2 hours)	Day 1	3 weeks (21 days)
Olaparib	It is prohibited to consume grapefruit, grapefruit juice and Seville oranges for duration of therapy. No routine prophylactic anti-emetic treatment is	150 mg	PO	BID, continuous	

	required; however, patients should receive appropriate anti-emetics in accordance with local treatment practice guidelines. Alternatively, olaparib tablets can be taken with a light meal/snack (i.e. 2 pieces of toast or biscuits).				
--	--	--	--	--	--

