#### 5.7 Duration of Follow-Up

Patients will be followed every 3 months for a minimum of 2 years from registration or until study closure or until death, whichever occurs first. As long as the study remains open with patients on treatment, patients will be followed for survival follow up for at least 2 years from the time of registration. If all patients have completed treatment, the study may be terminated for further follow up before the 2 years from registration for survival follow up for the last patients. Patients removed from treatment for unacceptable adverse events will be followed until resolution or stabilization of the adverse event.

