## 5.8 Off Study Criteria

Patients can be taken off study at any time at their own request, or they may be withdrawn at the discretion of the investigator for safety, behavioral or administrative reasons. The reason(s) for discontinuation from study will be documented and may include:

- Patient withdraws consent (termination of treatment and follow-up);
- Loss of ability to freely provide consent through imprisonment or involuntary incarceration for treatment;
- Patient is unable to comply with protocol requirements;
- Treating physician judges continuation on the study would not be in the patient's best interest;
- Patient becomes pregnant (pregnancy to be reported along same timelines as a serious adverse event);
- Development of second malignancy (except for basal cell carcinoma or squamous cell carcinoma of the skin) that requires treatment which would interfere with this study;
- Lost to Follow-up. If a research subject cannot be located to document survival after a period of 2 years, the subject may be considered "lost to follow-up." All attempts to contact the subject during the two years must be documented
- Termination of the study by The University of Michigan;
- Patient completes protocol treatment and follow-up criteria.

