**Paternal exposure**

Male patients should refrain from fathering a child or donating sperm during the study and for 5 months following the last dose.

All pregnancies in partners of male subjects occurring during the study participation or within 5 months of last dose must be reported to the Coordinating Center within the same time lines as for an SAE even if the patient was discontinued from the study.

Pregnancy of the patient's partners is not considered to be an adverse event. However, the outcome of all pregnancies (spontaneous miscarriage, elective termination, ectopic pregnancy, normal birth or congenital abnormality) occurring from the date of the first dose until 5 months after the last dose should, if possible, be followed up and documented.

The Coordinating Center will be responsible for reporting to Janssen Scientific Affairs, LLC and AstraZeneca within 24 hours of becoming aware of any patient or patient partner pregnancy using the Serious Adverse Event Form.

---

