  - Myelodysplastic syndrome/Acute myeloid leukemia (AML/MDS): occurred in <1.5% of patients exposed to olaparib monotherapy and the majority of events had a fatal outcome. Monitor patients for hematologic toxicity at baseline and monthly thereafter. Discontinue if MDS/AML is confirmed.
  - Pneumonitis: occurred in <1% of patients exposed to olaparib, and in some cases were fatal. Interrupt treatment if pneumonitis is suspected. Discontinue if pneumonitis is confirmed.
  - Embryofetal toxicity: olaparib can cause fetal harm. Advise of the potential risk to a fetus and to use effective contraception.

Women of childbearing potential and their partners, who are sexually active, must agree to the use of TWO highly effective forms of contraception in combination (as described in Appendix B). This should be started from the signing of the informed

---

consent and continue throughout the period of taking study treatment and for at least 6 months after last dose of study drug(s), or they must totally/truly abstain from any form of sexual intercourse (as described in Appendix B).

Male patients must use a condom during treatment and for 5 months after the last dose of olaparib when having sexual intercourse with a pregnant woman or with a woman of childbearing potential. Female partners of male patients should also use a highly effective form of contraception (as described in Appendix B) if they are of childbearing potential. Male patients should not donate sperm throughout the period of taking olaparib and for 5 months following the last dose of olaparib.

For details of acceptable methods of contraception refer to Appendix B Acceptable Birth Control Methods.

- **Drug Interactions:** Olaparib is increased with co-administration of strong or moderate CYP3A inhibitors. Conversely, olaparib is decreased with co-administration of strong or moderate CYP3A inducers. Olaparib is both an inhibitor and inducer of CYP3A and an inducer of CYP2B6.
- **Storage and stability:** Store at 20°C to 25°C (68°F to 77°F), excursions permitted to 15°C to 30°C (59°F to 86°F). Store in original bottle to protect from moisture.

Olaparib must be stored in a secure, limited access area.

- **Administration:**
  - See Section 5.1
- **Availability:** Provided by AstraZeneca.

Under no circumstance will the study medication (olaparib) be used other than as directed by the protocol. Do Not Use Commercially Available Product.

- **Return and Retention of Study Drug:**  

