**Appendix B      Acceptable Birth Control Methods****Olaparib is regarded as a compound with medium/high fetal risk.**

- Women of childbearing potential and their partners, who are sexually active, must agree to the use of TWO highly effective forms of contraception in combination [as listed below], throughout the period of taking study treatment and for at least 6 months after last dose of study drug(s), or they must totally/truly abstain from any form of sexual intercourse (see below).
- Male patients and their partners, who are sexually active and of childbearing potential, must agree to the use of TWO highly effective forms of contraception in combination [as listed below], throughout the period of taking study treatment and for 5 months after last dose of study drug(s) due to the unknown effects of the study drug on the sperm, or they must totally/truly abstain from any form of sexual intercourse (see below). Male patients should not donate sperm throughout the period of taking study treatment and for 5 months following the last dose of study drug(s).

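### Section 8.2.7 requires patient pregnancies to be reported for 5 months after last dose, one month less than the female contraception period, so a month-6 pregnancy after participation ends is not covered

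*Combined protocol and SAP*

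**What the plan says.** Section 8.2.7 sets the site's duty. A pregnancy in a study patient goes to the Coordinating Center on SAE timelines if it occurs during study participation or "within 5 months of last dose must be reported to the Coordinating Center", and discontinuation from the study does not remove that duty.

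The female contraception period is longer. Inclusion criterion 3.1.9 runs it from consent "to at least 6 months after the last dose of study treatment"; the synopsis, Section 9.2 and Appendix B give the same 6 months.

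For men the two periods agree. Under Paternal exposure in 8.2.7, "Male patients should refrain from fathering a child or donating sperm during the study and for 5 months following the last dose", and partner pregnancies are reportable over the same 5 months.

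Three other provisions decide who is still in participation at month 6:

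- Section 5.7 sets follow-up at a minimum of 2 years from registration, or until closure or death. It adds that, when nobody remains on therapy, "the study may be terminated for further follow up before the 2 years from registration for survival follow up for the last patients".
- Section 5.5 caps treatment at 18 months, and Section 5.1 states: "Protocol treatment must start within 14 business days of registration to the study".
- Section 5.8 makes pregnancy an off-study reason, with "pregnancy to be reported along same timelines as a serious adverse event".

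**The concern.** For women, the reporting duty stops a month before the precaution does. The female figure equals the male one and no reason is given for it, which suggests the male period was carried over.

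If a woman conceives in month 6 after her participation has ended, no text clearly obliges the site to report it. The protocol itself treats that month as one of possible fetal risk: it requires contraception then, Section 9.2 warns of fetal harm from olaparib, and Section 3.2.4 calls the teratogenicity of both drugs unknown. What could be lost is the report and the follow-up of that pregnancy to its outcome.

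**Working it through.** The plan gives no calculated figure to reproduce. The check compares stated periods and then asks who is exposed to the difference.

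**1. Contraception period against reporting window**

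| Group | Contraception after last dose | Reporting window after last dose | Difference |
|---|---|---|---|
| Female patients | 6 months (3.1.9, 9.2, Appendix B) | 5 months (8.2.7) | 6 − 5 = 1 month |
| Male patients and partners | 5 months (8.2.7, Paternal exposure) | 5 months (same place) | 5 − 5 = 0 |

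**2. A woman who stays in follow-up**

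She is covered at month 6 by the study-participation limb, provided participation includes follow-up. With the 18-month cap counted from registration, the end of month 6 falls at 18 + 6 = 24.0 months, exactly the 2-year minimum, so there is no overrun.

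**3. The same woman, with the cap counted from treatment start**

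Assume treatment starts at the 14-business-day limit and there are no public holidays.

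- 14 business days = 18 to 20 calendar days, or 0.59 to 0.66 months.
- Last dose: 18 + 0.59 to 18 + 0.66 = 18.59 to 18.66 months after registration.
- End of month 5: 23.59 to 23.66 months, inside the 24-month minimum.
- End of month 6: 24.59 to 24.66 months, 18 to 20 days beyond it.

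This needs a full course, the latest permitted start and follow-up that stops at its minimum.

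**4. A woman whose participation ends early**

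If the study closes at the last patients' final treatment, or a patient goes off study at last dose, months 0 to 5 are covered by the 5-month limb and none of month 6 is.

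**5. Whether other text fills the month**

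- The Coordinating Center must pass on any patient or partner pregnancy within 24 hours, but only once aware of it (8.2.7). The site duty that would make it aware is the one that stops at month 5.
- Section 8.2.2 lists drug exposure during pregnancy for expedited reporting but states no post-dose period.
- The 5.8 rule applies to patients still on study.
- Beyond 30 days after last dose, 8.1 and 8.6 call for SAEs considered related to treatment. Section 8.2.7 says pregnancy is generally not an adverse event, so this route reaches abnormal outcomes judged related and not the pregnancy itself.
- Scheduled contacts are not designed to detect it. The last planned pregnancy test is at the 30-day visit, follow-up calls document progression and survival (6.2, notes h and m), and the extra prompt in 8.1 concerns MDS/AML and new primary malignancies.

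No other provision sets a 6-month duty on the site.

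**The case against.** The strongest reply is that the same sentence in 8.2.7 already covers nearly everyone. Sections 5.6 and 5.8 imply that stopping treatment is not leaving the study and that follow-up is part of participation. A woman who stopped at 4.2 months, the median PFS on trabectedin alone in the cited phase III trial, would reach the end of month 6 at 4.2 + 6 = 10.2 months after treatment start, far inside follow-up. This stands, and it limits the point to patients who have left. Because participation is never defined, a site reading it as treatment only would extend the gap to every woman of childbearing potential, but that is the less natural reading.

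The exposed groups are also small. Early closure is a permission that concerns only the last patients. Loss to follow-up is declared only after 2 years. After consent is withdrawn, a longer window helps only if the site happens to learn of the pregnancy. All of this stands and bears on size. The 18-to-20-day overrun rests on several conditions together and deserves little weight.

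It can also be said that a reporting window need not equal a contraception period, that 8.2.7 asks for all pregnancies to be followed to outcome without repeating a time limit, and that related abnormal outcomes remain reportable. The first is fair: this is a gap in coverage and not a contradiction. The second is weak, because that sentence follows the one that sets the window. The third narrows the loss but leaves a month-6 pregnancy with a normal or unrelated outcome outside any clear duty.

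**Conclusion.** The point holds, as a minor one. The post-dose reporting window for patient pregnancies is one month shorter than the female contraception period, and a month-6 pregnancy after participation has ended falls outside the stated site duty. This assumes that participation includes follow-up. The exposed patients are those who leave the study early and, if the option in 5.7 is used, the last patients treated. A short overrun after a full 18-month course is possible only under the conditions in step 3. The documents do not allow a count of the patients affected. Sample size, decision rules and planned analyses are untouched; the value of a change lies in fetal-safety follow-up.

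**What to change.** In the patient-pregnancy sentence of 8.2.7, set the post-dose period for female patients to 6 months. Leave the 5-month period under Paternal exposure unchanged, since it already matches the male contraception period. The difference for women then becomes 6 − 6 = 0 months. The change is one sentence and can go into the next amendment; the burden is at most a few additional pregnancy reports.

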**Paternal exposure**

Male patients should refrain from fathering a child or donating sperm during the study and for 5 months following the last dose.

All pregnancies in partners of male subjects occurring during the study participation or within 5 months of last dose must be reported to the Coordinating Center within the same time lines as for an SAE even if the patient was discontinued from the study.

Pregnancy of the patient's partners is not considered to be an adverse event. However, the outcome of all pregnancies (spontaneous miscarriage, elective termination, ectopic pregnancy, normal birth or congenital abnormality) occurring from the date of the first dose until 5 months after the last dose should, if possible, be followed up and documented.

The Coordinating Center will be responsible for reporting to Janssen Scientific Affairs, LLC and AstraZeneca within 24 hours of becoming aware of any patient or patient partner pregnancy using the Serious Adverse Event Form.

---

**8.2.8 Overdose - Olaparib**

There is currently no specific treatment in the event of overdose with olaparib and possible symptoms of overdose are not established.

Olaparib must only be used in accordance with the dosing recommendations in this protocol. Any dose or frequency of dosing that exceeds the dosing regimen specified in this protocol should be reported as an overdose. The Maximum Tolerated Dose is 150 mg twice daily (tablet).

Adverse reactions associated with overdose should be treated symptomatically and should be managed appropriately.

- An overdose with associated AEs is recorded as the AE diagnosis/symptoms on the relevant AE modules in the CRF.

If an overdose on olaparib occurs in the course of the study, then the Investigator or other site personnel inform the Coordinating Center and appropriate AstraZeneca representatives immediately, or no later than 24 hours of when he or she becomes aware of it. The designated AstraZeneca representative works with the Investigator to ensure that all relevant information is provided to the AstraZeneca Patient Safety data entry site.

For overdoses associated with a SAE, the standard reporting timelines apply. For other overdoses, reporting must occur within 30 days.

### **8.3 Adverse Event Characteristics**

#### **8.3.1 CTCAE Term**

(AE description) and grade: The descriptions and grading scales found in the NCI Common Terminology Criteria for Adverse Events (CTCAE) version 5.0 will be utilized for AE reporting. All appropriate treatment areas should have access to a copy of the CTCAE version 5.0. A copy of the CTCAE version 5.0 can be downloaded from the CTEP web site. (<http://ctep.cancer.gov>)

